9.2 The Number of Participants

The planned sample size of 2200 patients is based on a high severity pandemic along a range of possible scenarios. This flexibility is important as the accuracy of the modelling may only become clear as the pandemic unfolds.

Based on data from the Department of Health, modelling estimates are that, for a high severity pandemic, 35% of those admitted to hospital will die and 25% will be admitted to intensive care. Of those admitted to intensive care, an estimated 50% will die (estimate derived from UK data related to the 2009 pandemic and to community acquired pneumonia). Thus 47.5% will have the composite outcome of death or admission to hospital in the control group. For this scenario, our study would have 90% power to detect a 15% reduction in relative risk of the composite outcome associated with steroids, and a 20% reduction in deaths. Since a high proportion of those admitted to hospital will die and admissions to intensive care will also be high, therefore, an effect size of 15% would be clinically important.

Table 2 presents a range of scenarios centres around a control event rate of 47.5%.

Control event rate	Relative risk reduction with dexamethasone treatment	N* (80% power)	N* (90% power)
35%	20%	1514	2006
	15%	2704	3592
40%	20%	1242	1644
	15%	2210	2932
47.5%	20%	940	1242
	15%	1662	2204
50%	20%	860	1134
	15%	1514	2010

Table 2: Sample size calculations for a high severity pandemic

* Sample size estimates in each cell have been inflated by 5%, to allow for lack of compliance and loss to follow-up (both anticipated to be low)

For low and moderate severity pandemics, a Hazard Ratio of 1.25, indicating an increased risk of discharge at any given time, is considered as the minimum clinically relevant change to detect. The sample size estimation method is the log rank test allowing for competing risks, and assumes that in the control group 5% are censored at 30 days, and in both groups, 6% (low severity pandemic) and 10% (moderate severity pandemic) die during hospitalisation. With 90% power and 1% two-side alpha, and allowing for 5% non-collection of primary outcome data, a total of 912 and 924 participants are required to be randomised for low and moderate severity pandemics respectively.

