The onset of symptoms is highly variable in influenza exposed adults¹ and the severity of symptoms is the result of a complex host-pathogen interaction² altered by co-infection and co-morbid illness³. Initially, cytokine data were used to describe this interaction, but recent data from a unique human influenza challenge study have fully described the human inflammatory and anti-inflammatory pathways that determine symptom severity in exposed adults⁴. Using whole genome arrays (Affymetrix Human Genome U133A v2), 5076 genes showed altered expression during the 5 days following influenza A exposure. Unsupervised and clinically informed analyses resulted in self-organising maps (clustered gene expression patterns) which showed 8 functionally important gene sets in which activation/inhibition was tightly associated with clinical severity (see reference 4). The study also described the duration in hours between virus exposure and significant difference in self-organising map (SOM) cluster expression between symptomatic/asymptomatic subjects.

Thus, this sub-study will apply the best contemporary (with respect to the time of pandemic declaration) methods to a representative sample (n=200) of ASAP trial participants in order to determine the interaction of steroid therapy and the host and to apply this in interpreting the clinical outcome measured.

[figure not shown]
Methods/Design

Patients recruited into the ASAP trial at the sub-study sites will be given the opportunity to participate in the sub-study. 200 patients who have received ASAP study medication are required for the sub-study.

ASAP trial participants who consent to participation in the sub-study will give two blood samples and have one nasal swab taken for subsequent transcriptomic and microbiological testing. Blood samples will be collected into vaccutainer tubes at baseline and 48 hours post first dose of ASAP study medication. These time points are practical and match the best available transcriptomic data and the expected time course of steroid effect on gene expression. These samples can be collected using standard venesection methods and transferred without urgency to frozen storage in the hospital clinical laboratories. These sample collections should therefore be minimally obstructive in the context of a pandemic. The nasal swab for virological confirmation will be obtained at the time of the first blood sample collection. Please see figure 1 for an overview of the sub-study design.

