The overarching principle in relation to the conduct of the mechanistic sub-study is that it should not disadvantage or jeopardise conduct of or recruitment into the main ASAP trial. Six sites have been selected to participate in the sub-study and the decision to activate the sub-study and these sites will be determined by the Trial Management Group according to pre-agreed criteria. The ability of these sites to conduct the sub-study will continue to be monitored by the Trial Management Group throughout the recruitment phase.

Figure 1: Overview of the sub-study design

* Blood and nasal samples are required at the latest 4 hours after first dose of study medication so consent must

have been obtained prior to the samples being taken.

[#] Sample should be obtained at 48 hours (+/- 3 hours) or at discharge if this is sooner

Participants and recruitment

All patients recruited into the ASAP trial at sub-study sites will be eligible to participate in the sub-study.

In order to fulfil the sampling requirements, recruitment into the sub-study should only be considered where it is practically possible to obtain consent for the sub-study and take the first blood sample required for the sub-study either before the participant receives their first dose of ASAP study medication or within 4 hours of the first dose of ASAP study medication being administered.

ASAP trial participants will be approached by a doctor or nurse following consent into the ASAP trial, either at the point of recruitment into the ASAP trial or shortly after being recruited into the ASAP trial.

Consent must be obtained for all patients recruited into the sub-study in a similar manner as for the ASAP trial to ensure a representative sample of participants.

A separate sub-study patient information sheet and consent form will be used.

The procedure for obtaining consent for the sub-study is as follows:

Patients with capacity to consent (non-emergency situation)

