For patients who lack capacity to consent at enrolment or patients with capacity that are entered into the trial under emergency situation regulations, written consent must be obtained by a doctor or an appropriately trained nurse from the participant (if capacity has been recovered) or Personal Legal Representative as soon as it is practicable to do so.

A Personal Legal Representative may be a partner, friend or relative.

The participant's decision to withdraw from the sub-study would overrule any decision made by a doctor or Personal Legal Representative.

Sampling requirements

Sub-study participants will give two blood samples and a nasal swab for sub-study purposes. All samples will be obtained by an appropriately trained doctor or nurse.

Table 1 provides a summary of the samples required.

Table 1: Sub-study samp le requirement s

Time point	Sample	Details	
	16 ml peripheral blood	2 x 2.5 PAXgene tubes (RNA expression analysis)	
Baseline		1 x 6ml plasma gel tube (corticosteroid pharmacokinetics)	
(after recruitment into ASAP trial and before, or within 4 hours of 1 st dose of ASAP		1 x 5ml serum gel tube (multiplex cytokine array)	
study medication)	Nasal swab	Collected in standard viral transport medium. This sample will be in addition to any nasal swab taken for clinical purposes, but may be taken at the same time-point if appropriate.	
Mid-treatment	20 ml peripheral blood	1 x 5ml plasma gel tube (corticosteroid pharmacokinetics)	
(48 hours (+/- 3 hours) after 1 st dose of study medication, or prior to hospital discharge,		1 x 5ml serum gel tube (multiplex cytokine array)	
whichever is sooner)		1 x 10ml EDTA tube (genotyping)	

Sample collection, storage and transport

Blood samples

A 16ml peripheral blood sample must be obtained before or within 4 hours of the first dose of ASAP study medication being given to the participant. Blood will be collected into 3 different tube types as outlined in Table 1. Of note, the PAXgene tubes should be collected last and should be used along with an extension adapter. Use of the adapter reduces the risk of reflux of the PAXgene preservative liquid during the blood draw.

A second 20ml peripheral blood sample must be obtained mid-treatment (at 48 hours (+/- 3 hours) after the first dose of ASAP study medication, or prior to hospital discharge, whichever is sooner).

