Analysis of samples will be performed in a single batch using either RNA microarray expression analysis or next generation sequencing, depending on which is the most cost-effective method to obtain the data needed at the time analysis is carried out. This is a fast-moving technology and while the current balance would still favour microarray, it is anticipated that this will no longer be the case in a few years.

An inflammatory array of genes expressed during acute influenza (+/- steroids) will be described (using microarray or sequencing technology). These data will inform the clinical severity score, the duration of illness and most importantly will confirm the immune-modulatory effect of steroids

Nasal swabs

The latest test available to detect influenza virus including the pandemic strain will be used; this is expected to be a PCR test, however the specific test cannot be determined until the point of trial activation. After testing, all nasal swabs will be disposed of.

Surplus samples

Consent will be sought from sub-study participants for any remaining samples to be stored and used for future ethically approved research. Where consent has been given remaining samples will be stored in under a storage license from the Human Tissue Authority (HTA). Request for access to these samples for future ethically approved research will be made through the Chief Investigator and lead sub-study Investigator. Any outputs arising from use of these samples must reflect the contributions of both study teams.

Data collection

No additional data over and above that collection for the ASAP trial is required for the sub-study.

Withdrawal

Each sub-study participant has the right to withdraw from the sub-study at any time. In addition, the investigator may withdraw a participant from the sub-study at any time if the investigator considers it necessary for any reason. Any samples already collected for the sub-study would still be used unless specifically requested not to, in which case any samples collected would be destroyed.

The reason for withdrawal from the sub-study will be requested and recorded in the trial database, however participants are not obliged to give reasons.

There will be no replacement of participants who withdraw from the sub-study.

Statistical analyses

Data arising from the sub-study will be analysed by sub-study investigators at the Liverpool School of Tropical Medicine and University Hospital Aintree.

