The following assumes that the platform chosen to achieve the stated aims is microarray analysis of the whole blood RNA transcriptome between subjects (placebo vs control) normalised to the transciptome of a set of healthy volunteers.

All analyses will be conducted in the latest version of R (currently 3.1.0). For analysis of the RNA transcriptome data we will use the latest version of the package Bioconductor (currently version 2.14). An initial normalisation step will be carried out to account for technical variation in the gene expression data between samples. Differential gene expression analysis will be explored between treatment and control samples using the normalised expression data.

- To address aim one, using day zero data, levels of expression of genes that defined temporal stage in the paper by Huang et al. will be summarised using appropriate descriptive statistics in order to define when in the course of flu infection patients were recruited to the study.
- To address aim two comparing steroid with placebo groups, between-group differences in the expression of relevant genes on day 3 will be estimated using appropriate regression models 4.
- To address aim three functional analysis of genes of interest (those that are differentially expressed between treatment and placebo groups) will be performed to infer the mechanism of action of steroid when given to patients with pandemic influenza; this will be a descriptive analysis.

References

- 1 F. Carrat, E. Vergu, N. M. Ferguson, M. Lemaitre, S. Cauchemez, S. Leach, and A. J. Valleron, 'Time Lines of Infection and Disease in Human Influenza: A Review of Volunteer Challenge Studies', *Am J Epidemiol*, 167 (2008), 775-85.
- 2 M. D. de Jong, C. P. Simmons, T. T. Thanh, V. M. Hien, G. J. Smith, T. N. Chau, D. M. Hoang, N. V. Chau, T. H. Khanh, V. C. Dong, P. T. Qui, B. V. Cam, Q. Ha do, Y. Guan, J. S. Peiris, N. T. Chinh, T. T. Hien, and J. Farrar, 'Fatal Outcome of Human Influenza a (H5n1) Is Associated with High Viral Load and Hypercytokinemia', *Nat Med*, 12 (2006), 1203-7.
- 3 M. B. Rothberg, and S. D. Haessler, 'Complications of Seasonal and Pandemic Influenza', *Crit Care Med*, 38 (2010), e91-7.

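### The second sub-study blood sample may be drawn at discharge before 48 hours, yet it is compared by arm as a day-3 sample and no draw time is provided for

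*Protocol*

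**What the plan says.** Appendix B describes the second blood sample in three ways.

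- Methods/Design gives a fixed time: "Blood samples will be collected into vaccutainer tubes at baseline and 48 hours post first dose of ASAP study medication".
- The footnote to the sub-study overview figure adds an exception: "Sample should be obtained at 48 hours (+/- 3 hours) or at discharge if this is sooner". Table 1 and the text on sample collection repeat it: "or prior to hospital discharge, whichever is sooner".
- Statistical analyses, under aim two, has a single steroid-versus-placebo comparison: "between-group differences in the expression of relevant genes on day 3 will be estimated using appropriate regression models".

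No part of Appendix B says whether samples drawn at an early discharge are kept, set aside or analysed separately. Under Data collection it states: "No additional data over and above that collection for the ASAP trial is required for the sub-study". The sample label is to encode a time point, but a recorded hour of the draw is not mentioned.

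Time to discharge is itself something the trial expects treatment to change. Section 5.2 has shorter stay as a secondary objective, and section 9.2 plans the low and moderate severity designs around "a Hazard Ratio of 1.25, indicating an increased risk of discharge at any given time".

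**The concern.** Appendix B treats gene expression as something that moves with time. It justifies the sampling times by the expected course of the steroid effect, and aim one uses expression to place each patient in the course of infection. A sample taken well before 45 hours is then not the same measurement as one taken at 45 to 51 hours.

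Steroid exposure differs as well. Under the dosing calendar in section 7.1.1, a 48-hour sample follows two or three doses, while a sample at an earlier discharge may follow only one.

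The exception also makes sampling time a post-randomisation variable that treatment may affect. If dexamethasone speeds discharge, slightly more of its samples are early, and patients who leave early are likely to be the milder cases. At stake is how the aim-two comparison, and the functional analysis under aim three that builds on it, can be interpreted. No primary or secondary outcome of the main trial is affected.

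**Working it through.** **No stated figure to reproduce.** The sub-study size of 200 comes without an effect size, alpha or power, and the protocol does not estimate how many samples would be early. The figures below are illustrative.

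**Inputs from section 9.2 (low and moderate severity).** In controls, 5% are still in hospital at 30 days. In-hospital deaths are 6% (low) or 10% (moderate). The discharge hazard ratio is 1.25. The lower edge of the sampling window is 48 − 3 = 45 hours, or 45/24 = 1.875 days.

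**Assumptions.** Hazards are constant, the hazard ratio applies in full from the first dose, and first dose is taken as the time of admission.

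**Control arm.** Total exit hazard λ = −ln(0.05)/30 = 0.0999 per day. By 1.875 days the share out for any reason is 1 − exp(−0.0999 × 1.875) = 0.1708.
- Low: discharges are 0.89/0.95 of exits, so 0.1708 × 0.937 = 16.0%.
- Moderate: discharges are 0.85/0.95 of exits, so 0.1708 × 0.895 = 15.3%.

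**Dexamethasone arm.** The discharge hazard is multiplied by 1.25 and the death hazard is unchanged.
- Low: discharge 1.25 × 0.0936 = 0.1169, death 0.0063, total 0.1232. Discharged: (0.1169/0.1232) × [1 − exp(−0.1232 × 1.875)] = 19.6%.
- Moderate: discharge 1.25 × 0.0893 = 0.1117, death 0.0105, total 0.1222. Discharged: (0.1117/0.1222) × [1 − exp(−0.1222 × 1.875)] = 18.7%.

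The differences are 19.6 − 16.0 = 3.6 and 18.7 − 15.3 = 3.4 points. With 100 per arm, about 34 to 36 of the 200 samples would be early, with 3 to 4 more in the dexamethasone arm.

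**Dependence on the assumed stay.** Take a 5-day median stay (an assumption) with 5% remaining at 30 days, and count all exits as discharges. A Weibull through those points (shape 0.82) gives 27% versus 32% before 45 hours. A lognormal through the same points gives about 18% versus 22%. More generally, for a control share f the dexamethasone share is about 1 − (1 − f)^1.25:

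| Control | Dexamethasone |
|---|---|
| 2% | 2.5% |
| 5% | 6.2% |
| 10% | 12.3% |
| 20% | 24.3% |
| 30% | 36.0% |

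**Shift in mean sampling time.** If early samples average 30 hours (assumed) and the rest 48, the arms differ by 18 hours times the difference in shares. For 16.0% versus 19.6% that is 18 × 0.036 = 0.6 hours. Across the table it runs from about 0.1 to 1.1 hours.

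**Which tubes the rule governs.** Table 1 assigns RNA expression to PAXgene tubes and lists them at baseline only. The mid-treatment tubes are plasma 5 ml, serum 5 ml and EDTA 10 ml. These add to the stated 20 ml, so the row is complete without an RNA tube. Read literally, the day-3 expression comparison has no sample.

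**The case against.** Several objections stand, at least in part.

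- Pooling is the plain reading, with one post-baseline sample and one comparison, but the protocol does not state it in words. The open reference to appropriate regression models could cover sampling time. That does not settle the matter, because no analysis plan can recover a draw time that was never recorded.
- A reader might infer that early samples cannot be told apart. The documents do not support this. The case report form takes discharge status (section 6.4.5) and in-hospital compliance from the medication chart (section 7.3), and section 16 has length of stay recorded in days. Early discharges can probably be identified to the day; what is lacking is hours since first dose.
- The day label is loose. Section 7.1.1 counts the date of first dose as Day 1, so a dose at 22:00 followed by discharge at noon two days later gives a 38-hour sample that still falls on Day 3. Aim one speaks of day zero.
- Discharge within two days also reflects baseline severity and bed pressure, not only response to treatment.
- Sampling at discharge retains patients who would otherwise be lost and keeps the randomised groups whole. The sampling rule is reasonable and need not change.
- Because Table 1 lists no mid-treatment RNA tube, the timing problem applies to expression only once that conflict is resolved.

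**Conclusion.** The point holds as a minor one. The protocol lets the second draw move to discharge, labels the comparison day 3, says nothing about earlier samples and provides for no draw time. Under constant hazards about 15% to 16% of control and 19% to 20% of dexamethasone samples would be early. Those figures rest on the low and moderate severity inputs. For the high-severity default, section 9.2 gives no discharge figures; the share should be smaller there.

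The main consequence is mixed sampling times and steroid exposure under one label, which adds noise and blurs interpretation.

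Two stronger readings are tempting. One is that a large part of any apparent steroid effect would be an artefact of unequal timing. The documents do not support that: the imbalance is about 3 to 4 points, and the mean timing difference about an hour or less. The other is that as many as a third of samples would be early. That needs a particular assumed stay distribution, and another curve through the same two points gives about a fifth.

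**What to change.** In Appendix B:

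1. **Data collection.** Record the date and time of the first dose and of the second draw for sub-study participants, and amend the statement that nothing further is required.
2. **Statistical analyses, main comparison.** Describe aim two as a comparison at 48 hours or at discharge if sooner. Keep all randomised sub-study participants. Do not adjust for sampling time, since treatment may affect it.
3. **Reporting.** Give by arm the number and timing of samples drawn before 45 hours.
4. **Sensitivity analysis.** Repeat the comparison in the 45 to 51 hour samples, weighted for remaining in hospital by baseline covariates, and note that this subset is selected after randomisation.
5. **Consistency.** Reconcile the mid-treatment row of Table 1, which has no RNA tube, with the planned day-3 expression comparison, and align the fixed 48-hour description and the day labels with the sampling rule.

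The timing changes cost two time fields for 200 participants and one extra analysis, with no extra visits or draws. The time fields must be in place before recruitment, since missing times cannot be reliably restored afterwards.

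### Appendix B collects RNA tubes only at baseline, yet plans a steroid versus placebo comparison of gene expression on day 3

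*Protocol*

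**What the plan says.** Appendix B (Methods/Design) describes two blood samples, one at baseline and one 48 hours after the first dose. It justifies these times because they "match the best available transcriptomic data and the expected time course of steroid effect on gene expression".

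The Statistical analyses section assumes "microarray analysis of the whole blood RNA transcriptome between subjects (placebo vs control" groups; the lines that follow show that the contrast meant is steroid versus placebo. It uses day-zero expression data for aim one. For aim two, "between-group differences in the expression of relevant genes on day 3 will be estimated using appropriate regression models". For aim three, it plans a functional analysis of the genes found to differ between the arms.

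The baseline row of Table 1, headed "16 ml peripheral blood", lists "2 x 2.5 PAXgene tubes (RNA expression analysis"), "1 x 6ml plasma gel tube (corticosteroid pharmacokinetics") and "1 x 5ml serum gel tube (multiplex cytokine array"). The mid-treatment row lists a 5 ml plasma gel tube for pharmacokinetics, a 5 ml serum gel tube for cytokines and a 10 ml EDTA tube for genotyping. The running text repeats the second total: "A second 20ml peripheral blood sample must be obtained mid-treatment". The instruction on how to draw the PAXgene tubes appears only in the paragraph on the 16 ml baseline sample.

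**The concern.** The analysis text needs RNA taken on treatment, and the sampling table provides none. The only RNA tube is drawn before the first dose or at most 4 hours after it, so it cannot show how expression differs between the arms two days into treatment.

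The comparison of expression between the arms is the mechanistic core of the sub-study. Aim three depends on it as well, because its functional analysis starts from the genes that differ. A missed tube cannot be recovered afterwards: the trial aims to recruit within one pandemic wave of about six weeks, samples stay at site until sub-study recruitment ends, and they are then analysed in a single batch.

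**Working it through.** **1. Is the tube list complete?** Tables read from a PDF can lose rows, so the first check is whether the listed tubes reproduce the stated volumes. All inputs are from Appendix B, Table 1.

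- Baseline: 2 × 2.5 (PAXgene) + 6 (plasma) + 5 (serum) = 16 ml. Stated: 16 ml.
- Mid-treatment: 5 (plasma) + 5 (serum) + 10 (EDTA) = 20 ml. Stated: 20 ml, in the table and again in the text.

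Both totals are reproduced exactly. The volume left at mid-treatment for an unlisted tube is 20 − 20 = 0 ml. A lost row is ruled out.

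**2. RNA volume at each time point.** Baseline: 2 × 2.5 = 5 ml. Mid-treatment: 0 ml. Adding the baseline PAXgene set to the second draw would make it 20 + 5 = 25 ml, which disagrees with the 20 ml in both places.

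**3. Can another tube serve?** The plasma and serum tubes are spun, divided and frozen for other assays. The EDTA tube is assigned to genotyping. The handling section describes RNA stabilisation for PAXgene tubes only and gives no handling for the EDTA tube.

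**4. Which draw is day 3?** Section 7.1.1 makes the date of the first dose Day 1 of treatment, so 48 hours later falls on Day 3. The sub-study analysis text calls baseline day zero. On that count 48 hours is day 2, and day 3 would be 72 hours, when no draw exists. Reading day 3 as the 48-hour draw is therefore an assumption, though the only one under which there is any blood sample at all. Participants who leave hospital earlier are sampled before discharge instead.

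**5. What each aim keeps.**

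| Aim | Needs | Available as written |
|---|---|---|
| (a) stage of infection at admission | Baseline RNA | Yes |
| (b) steroid effect, clinical phenotype | Main-trial data | Yes |
| (b) steroid effect, transcriptomic pattern | Day-3 RNA | No, 0 of 200 |
| (c) transcriptome, placebo versus steroid | Day-3 RNA and the genes that differ | No, 0 of 200 |

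Serum for the cytokine array is drawn at both times and is not affected.

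**The case against.** The best defence is that the intention is clear and the slip would be caught. Methods/Design justifies both time points by gene expression. Procedures are reviewed at least annually during hibernation and again in the 4 to 6 weeks of pre-activation. The sampling packs are assembled centrally in Liverpool, where someone must decide which tubes go in. The paragraph on PAXgene storage is not tied to a time point. All of this is true, and it means that a reader should not infer that the omission would surface only at batch analysis after the wave; the protocol does not support that. But none of these steps corrects the text. Table 1 is not a detail left open for a later manual: it gives a full tube list and a volume that exclude a second RNA tube.

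Two stronger readings are also tempting. One is that aims (b) and (c) both fail outright and that no post-dose expression could be seen at all. That goes too far. Aim (b) has a clinical part that survives, and because the baseline tube may be drawn up to 4 hours after the first dose, some of those samples may be post-dose. They would still not support the day-3 analysis.

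The other is that paired tubes would allow the day-3 comparison to be adjusted for baseline expression in everyone. The same 4-hour window rules this out. A tube taken after dexamethasone is not a pre-treatment covariate, and adjusting for it could remove part of the effect being estimated.

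**Conclusion.** The point stands as an internal contradiction in Appendix B. Table 1 and the collection text provide RNA at baseline only, while Methods/Design and Statistical analyses rely on RNA taken mid-treatment. As written, 0 of 200 participants would have a 48-hour RNA sample, and the transcriptomic part of aim (b) and the planned analysis for aim (c) cannot be carried out.

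This rests on two readings: that the EDTA tube is used as labelled, for genotyping, and that day 3 means the 48-hour draw. If day 3 meant 72 hours, there would be no blood sample of any kind.

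The defect is confined to an optional sub-study at six sites. The main trial's primary outcome, power and safety reporting are not touched. Within the sub-study it must be corrected before activation, because its central comparison cannot be made from the samples specified.

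**What to change.** Before the sub-study is activated:

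- Add PAXgene tubes to the mid-treatment row of Table 1, for example 2 × 2.5 ml as at baseline.
- Correct the 20 ml figure in the table and in the text, and any draw volume given on the sub-study information sheet. If nothing else changes, the draw becomes 25 ml. Because genotype does not change with time, the EDTA tube can instead be reduced (a 5 ml tube would keep the draw at 5 + 5 + 5 + 5 = 20 ml) or moved. Moving it to baseline makes that draw 16 + 10 = 26 ml and the second draw 20 − 10 + 5 = 15 ml.
- Extend the PAXgene collection instructions (order of draw, adapter) to the second draw.
- Use one day count throughout, so that day zero, day 3 and 48 hours agree.
- Limit any adjustment for baseline expression to samples confirmed as taken before the first dose, which requires the times of the draw and of the first dose.

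The cost is 200 × 2 = 400 extra tubes, up to 200 further RNA extractions and assays, and a slightly larger draw. The protocol gives no budget, so whether that processing is already funded cannot be told. No extra venepuncture is needed.
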